8.3.7 Reporting of Pregnancy

Pregnancy and not using effective contraception are exclusion criteria for participation. Medications used in the study are Class C, i.e. their effects on pregnancy are not well known. In addition to pregnancy urine test conducted as part of screening, pregnancy will be monitored using betaHCG test prior to MRI scans and by self-report during follow up and treatment visits. When a pregnancy has been confirmed in a subject, and the fetus is exposed to study drug and/or process maternally, participant will be excluded from participation and referred to her treating physician for monitoring.

9 STATISTICAL CONSIDERATIONS

9.1 Statistical Hypotheses

Overview of primary hypotheses: Our primary response will be a binary indicator of treatment failure on the XRNTX or XRBUP regimen, defined as ≥ 2 weekly UDS positive for opioids, or self-report of ≥ 2 periods of three or more days of opioid use, or refusing XRNTX or XRBUP, or dropping out of study entirely. In hypotheses H1a and H1b, we are examining the effects of small, pre-specified, sets of measures, so our analyses will focus on model fit and prediction, and not on model selection. In hypothesis H1c, we search for best sets of predictors among demographic and clinical-behavioral variables, and over sets of brain/neural measures, so our focus is on model selection and on avoiding overfitting to the available data.

R61 Phase:

Hypothesis H1 (fMRI): For each of the cue reactivity (H1a), response inhibition (H1b), and connectivity (H1c) brain measured, we have a small number of neural responses associated with one or two regions of interest. These variables are continuously distributed, so we will test Hypotheses 1a, 1b and 1c using a repeated measures analysis of variance (rm-anova). The models will include a within-subject factor for Session (PRE vs ON) and a between-subject factor Group (XRNTX vs XRBUP), and their interaction. To accommodate the anticipated non-normal distributions of the response, we will use a generalized estimating equation (GEE) approach, using robust standard errors, using a compound symmetry working correlation structure for the within-subject correlations between the PRE and ON fMRI scans (Diggle PJ et al 2002). We will perform the rm-anova separately for each ROI (mPFC and VS for H1a, IFC for H1b, and VS-rtIFG and VS-mPFC for H1c). The hypotheses will be addressed by the Session by Group interaction, and we will obtain estimates and standard errors of the PRE vs ON change within each of the two groups, along with the size, standard error and significance of the differences between these estimates.

Sample size considerations for sample: The sample size is adequate for application of the GEE methods to obtain robust standard error (Lipsitz et al 1994). For a test of the PRE vs ON effect, our sample yields 80% power for a one-sided test that the ON levels will be Cohen's $d=0.4$ lower than the PRE levels, consistent with a decrease of Cohen's $d=0.5$ observed in our preliminary data and a decrease of Cohen's $d=0.3$ in the Suboxone sample.

Milestone for transition from Phase 1 to Phase 2: Using the models described above, we will obtain (model-based) estimates of the Session (PRE vs ON) by Group (XRNTX vs XRBUP) effects for the five hypotheses described above. If these estimates show at least small effects (Cohen's $d \geq 0.2$) in at least two of the three domains, then we will continue to the R33 phase.

Primary Analyses for Phase 2: Session by Group interaction effects on neural response: First, we will formally test the interaction effects explored in the R61 phase. We will rerun the analyses described for H1a, H1b and H1c in the R61 phase, for the full sample of $n=140$ obtained through the R61 and R33 phases. The models will be exactly as described in the R61 phase.

Effects of neural response on relapse vulnerability: Our primary outcome combines adherence to treatment and frequency of illicit opioid use during treatment. The primary outcome is a binary indicator of treatment success: if a patient provides ≥ 2 weekly UDS positive for opioids, or self-report of \geq two or more periods of ≥ 3 days of opioid use, or refuses XRNTX or XRBUP, or drops out of treatment entirely, then they will be classified as a treatment failure; otherwise they will be classified as a treatment success. We will calculate the PRE-ON change in %-signal-change for each of the regions and neural responses described in the R61 phase. We will use logistic regression models to predict the log-odds of treatment success (Aitkin et al 2009). The predictors in the model will be a binary factor for Group (XRNTX vs. XRBUP), and the neural change scores. We anticipate that there will be some greater PRE to ON changes in the XRNTX group than in the XRBUP group, so there will be some confounding between the effects of change score and the effects of Group on the rates of positive UDS. Thus, we will include Group first in our model, so evaluating the Group effect separate from the change-score effects, and then include the change scores in a model including Group, so evaluating the additional effect of change-scores in addition to the existing effects of Group. To assess whether the effects of the change scores differ between the XRNTX and XRBUP groups, we will also test for interaction effects between Group and each of the change-scores, by adding the interaction terms to the model that includes the group and neural change score main effects. We will check the assumptions underlying the logistic regression models (e.g. linearity of covariates effects on log-odds, outliers, influential observations) using standardized residuals, influence diagnostics, and graphical displays.

Sample size considerations for the sample: Analyses of Session by Group effects on neural response: For a one-sided test that the PRE vs ON effect is larger in the XRNTX group than in the XRBUP group, our sample of 70 per group yields 81% power for an effect of $d=0.42$ or greater. This effect is similar to the effects observed in the preliminary data. On the basis of the preliminary data we anticipate Group by Session effects of approximately $d=0.38$ in the VS and $d=0.42$ in the mOFC.

Analyses of effects of neural response on relapse vulnerability: We consider the effect for an individual neural change variable, in a model where Group is included, assuming a small effect for Group (odds ratio = 1.25). We have three domains, with two neural variables in two domains and one in the other, so we provide power for $\alpha=0.05$ and for $\alpha=0.025$. For $\alpha=0.05$ we have 80% power for an odds ratio of 1.75 or higher per standard deviation increase in a neural variable; for $\alpha=0.025$, we have 80% for an odds ratio of 1.86 or higher.

Analyses of polysubstance use outcomes: We will also examine the effects of Group and neural change variables on other substance use outcomes, including self-report and UDS measures of opioid, stimulant, and benzodiazepine use. Here, we will use the self-report and UDS measures to create binary weekly measures of use for each substance, and use GEE repeated measures logistic regression models, with Group and the neural change measures as predictors, to estimate and test effects. These secondary analyses will be subject to missing data. We anticipate 25% dropout rates. To assess possible effects of nonignorable missingness on inference, we will perform sensitivity analyses using pattern-mixture models and selection models. For pattern mixture models, subjects are grouped on the basis of their pattern of missing data, and the resulting categorical factor is included in the analyses as a main effect and interaction with predictors of interest. Overall predictor effects may be found by averaging over the patterns (Molenberghs et al 2005). Selection models (Molenberghs et al 2005) take a different approach, by explicitly modeling the probability of drop out, and incorporating the predicted probabilities into the main longitudinal analysis, with the dropout and response processes included in a single bivariate model. Comparisons between the predictions of the primary analyses, and each set of pattern mixture and selection models, provides some evidence for assessing the sensitivity of results to missing data.

Predictive modeling: The models for relapse/treatment-success addressed the effects of neural responses, in isolation from demographic and clinical measures. In further analyses, we will examine their effects in combination with demographic and non-imaging clinical predictors. As we can expect overlap between the effects of these sets of variables, we compare the effects of these domains on prediction of treatment success. Thus, we will compare models using various sets of predictors on the basis of AUC comparisons, rather than on goodness of fit (Sullivan Pepe 2003). In our model search, we will compare models containing interactions between Group and the various predictors, with the constraint that an interaction is included only in models where the corresponding main effects are also included. First, we will find the best fitting demographic model, searching over a set including age, race, gender, and educational status. Next, with the predictors from the best demographic model included, we will search over the clinical predictors (depression and anxiety scores, measures of withdrawal and craving, and the ASI composite scores) to find the set that most improves the predictive utility of the best demographic model. Third, with the predictors from the best demographic/clinical model included, we will search over the measures of neural change to find the set that most improves the fit of the best demographic/clinical model. We will then perform goodness of fit and ROC comparisons between the best demographic, demographic/clinical, and demographic/clinical/brain models. This process involves three searches over various sets of variables, and unconstrained searches are likely to yield complex models involving many predictors, resulting in a prediction rule that performs poorly in new samples. To avoid this, we will use a lasso approach to fitting the logistic regression models for this hypothesis. The usual algorithms for logistic regression estimate the model parameters by minimizing a measure of lack of fit of the model to the data, but do not penalize models for complexity. The lasso approach selects a best fitting model subject to the constraint that the sum of the magnitudes of the regression coefficients in the model is less than a small positive threshold value. The threshold is chosen adaptively from the data, by minimizing an estimate of the prediction error for the model, using ten-fold cross validation. Then, a best fitting model is chosen with the estimated threshold used in the penalty. The best fitting model is usually one in which a number of the coefficients are set to zero, i.e. a number of predictors are dropped from the model.

9.2 Sample Size Determination:

Analyses of Session by Group effects on neural response: For a one-sided test that the PRE vs ON effect is larger in the XRNTX group than in the XRBUP group, our sample of 80 per group yields 81% power for an effect of $d=0.42$ or greater. This effect is similar to the effects observed in the preliminary data. On the basis of the preliminary analysis, we anticipate Group by Session effects of approximately $d=0.38$ in the VS and $d=0.42$ in the mOFC.

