Neuroimaging (MRI): The MRI session will take place after detoxification and immediately before MAT induction (Table 1, Figure 1). This baseline time-point has been used successfully in our prior studies (Langleben et al 2014, Wang et al 2015) Participants will be escorted to the MRI facility where the investigator will meet them, review the consent and MRI screening form, and answer any remaining questions. Participants will be placed in the scanner in a supine position. The stimuli are rear projected to the center of the visual field using a PowerLite 7300 Video projector system (Epson America, Inc.) and viewed through a mirror mounted on the head coil. Participants will be given a non-ferromagnetic scroll wheel (FORP™, Current Design Inc., Philadelphia, PA) to respond during the tasks. Neuroradiologists will review the scans for clinically significant abnormalities. fMRI data will be acquired during (a) MPRAGE T1 image acquisition (5 min), (b) resting-state fMRI (5 min), (c) Go-NoGo task (5.5 min), (d) visual opioid cue task (10.5 min). The Go-NoGo and the visual opioid cue task will be counterbalance between scan 1 and 2. The total time in the scanner, including time for positioning removal and structural imaging, will not exceed 60 minutes.

STUDY MEASURES: will be administered by the study coordinator or psychologist with appropriate level of clinical training and certification (MA, PsyD or PhD):

Demographic and Clinical (Appendix Section 12.1): We use PhenX protocols (phenxtoolkit.org).

Demographical Information: Standard demographical information will be collected during phone screening and baseline study appointments, such as height, weight, preliminary fMRI eligibility, contact information, years of education etc.

MINI International Neuropsychiatric Interview (MINI) (Sheehan DV, 1998; 59(suppl 20)). The MINI is a clinician administered neuropsychiatric interview for symptoms across 17 of the most common mental health disorders. The DSM-5 version of the MINI will be administered.

Addiction Severity Scale Lite (ASI-Lite) (McLellan, 1997) The Addiction Severity Scale Lite is a shortened version of the full clinical interview. The measure collects information on demographics, employment, legal status, alcohol/drugs, family/social relationships, and psychiatric status. This measure is administered by a clinician.

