6.3 Measures to Minimize Bias: Randomization and Blinding

Urn Randomization. We plan to use urn randomization to stratify subjects across the two treatment conditions. We will stratify subjects on sex on the day of randomization.

An off-site statistician will work with clinical research staff in setting up the urn randomization sequences and will ensure that the codes linking subject's ID numbers to treatments are secure. Randomization uses an electronic emergency-unmasking database in Microsoft Access accessible to the off-site statistician 24 hours a day.. Randomization tables are secured within Microsoft Access and are managed by an off-site statistician and data management study personnel, who do not work directly with study participants. The system only provides access for one subject at a time and all transactions are recorded. If a subject is prematurely discontinued from the trial, all attempts will be made to not break the blind. If an emergency necessitates that the blind be broken, only the off-site statistician will have access to the blind to do so. They will be given the name of the staff members who have authority to request that the blind be broken. The off-site statistician can be reached 24 hours a day and can access a subject's code rapidly.

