9.4 Statistical Analyses

9.4.1 General Approach

Data Management. Data will be gathered using Penn's REDcap data collection system, a direct-entry data system where subjects can directly enter responses. REDcap is HIPAA compliant and data is secured on Penn Medicine's data management unit (DMU) network. Interview data and self-report data are entered directly into REDcap at the research sites, by research technicians and study subjects respectively. Field validation (eg, no out of range or otherwise invalid responses will be accepted) and form validation (e.g. logically impossible responses to different questions will not be accepted) are built into this entry process. Data are transmitted (128-bit encrypted form) over the internet to the DMU servers. After online reviews, the data are archived on the servers. Certain DMU staff members have permission to modify the archived data. Audit logs record any modification to the original entry. Password protection allows members of the research team appropriate levels of data access. At time of data collection clinical research staff will review data collected for completeness (field and form validation). Weekly routine data inspections will be performed by clinical research staff to ensure data integrity. Subject brain scan data are extracted via CAMRIS web-servers and are archived to lab-specific, encrypted servers for standard cleaning and analysis.

Data Analyses. [name], the CSA Statistician, and his staff will perform the data analyses. Prior to analyses, standard data screening/cleaning procedures will be applied ⁵³. These procedures will screen the data for data-entry errors, check for outliers, assess the extent and pattern of missing data, and check that appropriate assumptions of normality are met whenever necessary. Due to sample size, it is unlikely that the randomization will result in significant imbalance of the distributions of demographic or other variables across treatment groups. Additional covariates will be considered for inclusion in the analyses, to improve the precision of estimation for the treatment effects. Covariates describing levels of cocaine use prior to the study may be included. Assumptions underlying the application of statistical methods will be examined, through use of standardized residuals, influence diagnostics, and graphical displays.

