13 APPENDIX

13.1 Schedule of Activities (SoA)

	Screening detox and randomization (Day -14)	MRI Scan 1 Baseline (day 0)	Induction to XRBUP or XRNTX (day 0-10)	Injection 1 (day 10) + weekly follow up	Injection 2 (day 40)	MRI Scan 2 On Treatment (day 55)	Injection 3 (Day 70)	Weekly Follow- up End of study and referral (Day 100)
Psychiatric and medical								
Demographics (age ¹ , sex ¹ , edu ¹)		X						
History, physical and labs (C.4.a)		X						
SILS		X						
MINI (EOS* – end of study)		X						X EOS*
Addiction Severity Index ¹		X						X EOS*
Clinical/Behavioral (C.3.a)								
HAM-D ² , HAM-A ² , COWS ²	X	X	X		X	X		X
SOWS, Opioid Craving Scale ² , SF-MPQ-2 ² , STAI-6		X	X	X	X	X		X
TLFB interview	X	X	X		X	X		X
Ten-drug urine drug screen (UDS)	X	X	X	X	X	X		X
Go-NoGo errors of commission ²		X		X				
Neuroimaging (Section C.3.b)								
Go-NoGo fMRI ³		X			X			
Opioid Cue task fMRI ³		X			X			
Resting-state fMRI ³		X			X			
MPRAGE (anatomical MRI scan)		X			X			

PRINCIPAL INVESTIGATOR SIGNATURE

STUDY SPONSOR: [name]

STUDY TITLE: **Open label comparison of injectable extended release preparations of buprenorphine (Brixadi®) and naltrexone (Vivitrol®) for the treatment of opioid use disorder**

STUDY ID 843403

PROTOCOL VERSION V5.0

I have read the referenced protocol. I agree to conduct the study in accordance to this protocol, in compliance with the Declaration of Helsinki, Good Clinical Practices (GCP), and all applicable regulatory requirements and guidelines.

Principal Investigator Name	[name]	Signature
Affiliation:	University of Pennsylvania	Date 7/17/2023

END OF DOCUMENT

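### The confirmatory Group-by-Session test leaves the PRE scan out as a covariate; adjusting ON for PRE would be more precise at no data cost

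*Combined protocol and SAP*

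**What the plan says.** The primary endpoint in the Synopsis (Section 1.1) is the Group-by-Session interaction in the fMRI signal. Section 9.1 tests it separately for five measures: mPFC and VS for cue reactivity, IFC for Go-NoGo, and VS-rtIFG and VS-mPFC connectivity. It uses a GEE with robust standard errors and a compound-symmetry working correlation. The model terms are: "The models will include a within-subject factor for Session (PRE vs ON) and a between-subject factor Group (XRNTX vs XRBUP), and their interaction". PRE therefore enters as one of two outcome values, not as a covariate. For the confirmatory analysis of 140 participants, Section 9.1 adds: "The models will be exactly as described in the R61 phase".

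On power, Section 9.1 says "our sample of 70 per group yields 81% power for an effect of" d=0.42, one-sided, and anticipates d=0.38 in the VS and d=0.42 in the mOFC. Section 9.2 gives the same 81% for 80 per group.

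Section 9.4.1 says: "Additional covariates will be considered for inclusion in the analyses, to improve the precision of estimation for the treatment effects". The only covariate it goes on to name is prior cocaine use, and that only as a possibility. The PRE signal is not named as a covariate anywhere.

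On timing, Section 6.1 says of the baseline scan: "The MRI session will take place after detoxification and immediately before MAT induction". The Schedule of Activities (Section 13.1) heads its first column "Screening detox and randomization (Day -14") and puts Scan 1 at day 0. Section 6.3 says of the urn randomisation: "We will stratify subjects on sex on the day of randomization".

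**The concern.** A difference in raw change subtracts the whole of each participant's PRE value. When PRE and ON are imperfectly correlated, that adds PRE noise to the comparison. Regression of ON on Group and PRE removes only the predictable part, so it is more precise whenever r is below 1 and the two variances are equal.

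The plan has little power to spare at its own effect sizes. With 70 per group and every scan complete, power is about 80% at d=0.42 and 72% at the d=0.38 expected in the VS. The PRE scan is taken before any study medication, so the adjustment needs no extra data. The general remark on covariates in Section 9.4.1 does not settle the matter. Set beside a confirmatory model fixed exactly as in Phase 1, it leaves PRE either out or open to a later choice.

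**Working it through.** **Inputs.** From Section 9.1: 70 per group, one-sided, d=0.42 and 0.38. From Section 9.2: 80 per group. The 25% dropout rate is stated in Section 9.1 for the polysubstance outcomes ("We anticipate 25% dropout rates"). *Assumed, because not given:* one-sided alpha of 5%, equal PRE and ON variances, and r = 0.3, 0.5, 0.7 or 0.9. The SD that standardises d is not stated, so both readings are shown.

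**1. The plan's own figure.** Treat the interaction as a two-sample comparison of change scores, with d in change-SD units. The noncentrality is d·√(n/2) = 0.42·√35 = 2.485 on 138 df, which gives 79.6% (normal approximation 79.95%), close to the stated 81%. One-sided 2.5% gives 69.4% and does not reproduce it. For d=0.38 the noncentrality is 2.248 and power is 72.3%.

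**2. What the interaction estimates.** In simulated trials with complete pairs, the GEE interaction equalled the difference in mean raw change every time (maximum discrepancy 0).

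**3. Variance ratio, complete data.** With unit variances, the change score has variance 2(1−r) and the PRE-adjusted residual has variance 1−r². The ratio is (1−r²)/[2(1−r)] = (1+r)/2, that is 0.65, 0.75, 0.85 and 0.95.

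**4. Power, complete data, d in change-SD units.** Multiply d by √(2/(1+r)) and use one df fewer.

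| Per group, d | Planned | r=0.3 | r=0.5 | r=0.7 | r=0.9 |
|---|---|---|---|---|---|
| 70, 0.42 | 79.6% | 92.2% | 88.7% | 85.0% | 81.4% |
| 70, 0.38 | 72.3% | 87.1% | 82.6% | 78.3% | 74.2% |
| 80, 0.42 | 84.1% | 94.9% | 92.1% | 88.9% | 85.7% |

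**5. Power with 25% of ON scans missing at random.** Let N=70 per arm have PRE and m = 0.75·70 = 52.5 have ON. The planned GEE keeps PRE-only participants, and the regression drops them. Per arm:

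- GEE: 1/N + 1/m − r²(1/m − 1/N) − 2r/N
- Regression: (1−r²)/m

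At r=0.5 these are 0.01786 and 0.01429, a ratio of 0.80.

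| | r=0.3 | r=0.5 | r=0.7 | r=0.9 |
|---|---|---|---|---|
| Variance ratio | 0.71 | 0.80 | 0.88 | 0.96 |
| GEE power, d=0.42 | 72.3% | 71.3% | 70.3% | 69.4% |
| Regression power, d=0.42 | 84.3% | 79.5% | 75.0% | 70.8% |

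A simulation of 8,000 runs with the exchangeable correlation estimated gave ratios of 0.71, 0.81, 0.89 and 0.98.

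**6. If d is in raw-SD units.** With complete data, 70 per group and d=0.42, power goes from 67.2% to 82.8% (r=0.3), 79.6% to 88.7% (r=0.5) and 93.9% to 96.5% (r=0.7). At r=0.9 both are about 100%.

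**7. Sex.** A sex main effect cancels from the interaction. Adding it to the complete-data GEE moved the estimate by 0.0, so no precision gain is claimed for it.

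**The case against.** The plan is coherent as it stands. The endpoint, the H1 hypotheses, the within-group estimates, the H2a predictors and the power statement are all framed as change, and the test is valid. That is correct, which is why this is a recommendation about precision only.

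The size of the gain is uncertain. Neither r nor the unit of d is given, and complete scans are the favourable case. Section 4.1 cites 50% to 75% retention at the third XRNTX injection. If half the ON scans were missing at random, the step 5 formulas give variance ratios of 0.79, 0.86, 0.92 and 0.97, and gains of about 9, 6, 3 and 1 points at d=0.42. The gain shrinks but stays positive. With 80 per group and complete scans, planned power is already 84% at d=0.42, though still 77% at d=0.38.

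The most substantial objection is comparability at PRE. Section 6.1 says randomisation follows abstinence, so the Schedule's column heading does not by itself fix randomisation at Day -14. Neither place says whether Scan 1 comes before randomisation, and the study is open label. Section 7.2 allows replacement of participants randomised but not injected, and Section 9.3 analyses only those treated. The arms also have different inductions, so the analysed groups could differ at PRE. With equal variances, a systematic PRE difference of delta separates the two estimates by (1−r)·delta. This caveat stands. It governs how the adjusted result is reported and does not remove the precision argument.

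**Conclusion.** The concern holds. The confirmatory model omits the PRE signal as a covariate, and no other section commits to it. The planned test is valid but gives up precision. The direction holds for any r below 1 with equal variances. In large samples, the adjusted estimate is never less precise than the change score when pairs are complete. The size depends on assumptions. At one-sided 5% with 70 per group and d=0.42, the gain runs from about 16 points (r=0.3, raw-SD units, complete scans) down to 2 points or less at r=0.9. With 25% of ON scans missing at random and d in change-SD units, it is about 12, 8, 5 and 1 points across r = 0.3 to 0.9. For the VS at d=0.38, with complete scans and change-SD units, adjustment lifts power from 72% to above 80% if r is 0.5 or lower.

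**What to change.** - **Primary Phase 2 test.** For each of the five measures, pre-specify a regression of the ON signal on Group and the PRE signal, with robust standard errors. Include sex because randomisation is stratified on it.
- **Supportive analysis.** Keep the unadjusted Group-by-Session GEE for support, for the Phase 1 milestone and for the within-group changes.
- **Scan order.** State whether Scan 1 precedes randomisation and disclosure of assignment, and reconcile Section 6.1 with the Schedule of Activities. Only if it does may a longitudinal model with a common PRE mean be used to retain PRE-only participants. If it does not, report both estimates. Compare PRE between arms in the treated population in either case.

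**Cost.** SAP wording and no new data. The endpoint is worded as an interaction and needs a small restatement. The milestone metric and the H2a change scores can stay. The regression drops participants without an ON scan, whom the GEE keeps; the step 5 figures already include that loss. Because Phase 1 participants are part of the confirmatory sample, the amendment should record whether Phase 1 between-arm estimates had been seen when it was made. If r is near 0.9, the return is about 2 points of power at most.
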